8.4.2 Proportion of patients endpoint analyses

Secondary endpoints assessing proportion of patients fulfilling an event will be compared between treatments using a logistic regression model adjusting for treatment. The difference between treatment arms will be expressed as a difference in proportions as measured by the Cochran Mantel-Haenzel (stratum)-weighted estimator based on the fitted logistic regression model. The delta method will be used to calculate the standard error for the difference and the associated confidence interval. For endpoints with a low number of events, the baseline disease state will be dropped from the model. In addition, the raw proportions per treatment group will be given. If 0 events in any of the groups only raw proportions will be given.

- Proportion of patients who are in a recovery state (Days 29 and 60).
- Proportion of patients with improvement of one category using the WHO ordinal scale (Days 10 and 29).
- Proportion of patients with improvement of two categories using the WHO ordinal scale (Days 10 and 29).
- Proportion of patients in use of oxygen (Days 10 and 29).
- Proportion of patients alive and not in respiratory failure (invasive mechanical ventilation or ECMO (Days 10 and 29).
- Proportion of patients receiving non-invasive ventilation (Days 10 and 29).
- All-cause mortality

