6.1 Inclusion Criteria

Participants are eligible to be included in the study only if ALL of the following criteria apply:

Type of Participant and Disease Characteristics

- Male or Female
- Age ≥ 18 years
- Proven SARS-CoV-2 infection (confirmed by PCR from a nasopharyngeal or lower respiratory tract sample or antigen testing from a nasal sample)
- A score of Grade 3 to 5 on the WHO 9-point Ordinal Scale
- Male participants must agree to use a highly effective contraception as detailed in [Appendix 5](#) during the treatment period and for at least 4 days after the last dose of study treatment and refrain from donating sperm during this period
- Female participants are eligible to participate if not pregnant; not breastfeeding; and at least one of the following conditions is met:
 - Not a woman of childbearing potential as defined in [Appendix 5](#)

OR

- A woman of childbearing potential who agrees to follow the contraceptive guidance in [Appendix 5](#). During the treatment phase and for at least 4 days after the last dose of study medication
- Capable of giving signed informed consent which includes a commitment to comply with the requirements and restrictions listed in the informed consent form (ICF) and within this protocol.

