7.2 Method of Treatment Assignment

All participants will be randomized via a random allocation to alvelestat or placebo arms to meet enrolment needs of the study. The randomization numbers will be linked to the 2 treatment regimens, and the randomization scheme will not be stratified

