9.3.1 Effect on disease progression recorded as participant status

- Alive and free of respiratory failure
- Alive with respiratory failure (need for high-flow oxygen, Extracorporeal Membrane Oxygenation (ECMO), non-invasive or invasive mechanical ventilation

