9.3.2 WHO 9-Point Ordinal Scale

Each assessment will be recorded as a number in the CRF based on the status categories below. Where possible the timing of each assessment should be similar (i.e. morning or evening throughout)

0. Uninfected, no clinical or virological evidence of infection
1. Ambulatory, no limitation of activities
2. Ambulatory, limitation of activities
3. Hospitalized – mild disease, no oxygen therapy
4. Hospitalized – mild disease, oxygen by mask or nasal prongs
5. Hospitalized – severe disease, noninvasive ventilation or high flow oxygen
6. Hospitalized – severe disease, intubation and mechanical ventilation
7. Hospitalized – severe disease, ventilation and additional organ support – vasopressors, renal replacement therapy, extracorporeal membrane oxygenation
8. Death

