6.2 Endpoints

Clinical study endpoints and associated definitions are listed in Table 3.

Table 3. COSTA clinical study endpoint definitions.

Endpoints	Definitions	
Primary	To evaluate the safety and tolerability of alvelestat administered twice daily (bid) for 5 or 10 days	
By treatment group (alvelestat/placebo):
 
 • Numbers and % of subjects who experience at least 1 treatment-emergent adverse event to Day 60 (Safety Outcome Assessment) • Adverse events of special interest (liver function abnormalities, corrected QT interval, infections, and neutropenia) and clinically significant safety monitoring labs tests to EoT • Number and % of subjects that discontinue alvelestat to Day 5 or 10 • Number and % of subjects requiring dose reduction to Day 5 or 10 • Number and % of subjects with AE of headache on prospective questioning and CTCAE severity Grade to Day 5 or 10 • Change in vital signs, EKG, safety laboratory measures to Day 5 or 10 or EOT
Secondary	To evaluate the effect of alvelestat on blood pharmacodynamic markers of Neutrophil Extracellular Trap (NET) activation, elastase, inflammatory and coagulopathy activity	
By treatment group (alvelestat/placebo), change from baseline to Day 5 or 10 in:
 
 • Blood biomarkers of NETosis (cell-free DNA; citrullinated histone H3; Myeloperoxidase (MPO)-DNA complexes) • Blood biomarkers of inflammation (absolute neutrophil count; absolute lymphocyte count; neutrophil-lymphocyte ratio [NLR], C-Reactive protein, procalcitonin) • Pro-inflammatory cytokines IL-1beta, IL-6, IL-8, TNF-alpha) • Coagulopathy as measured by D-Dimer • Plasma desmosine/isodesmosine
	To explore the effect of alvelestat on pulmonary function	
By treatment group (alvelestat/placebo):
 
Proportion of subjects alive and free of respiratory failure (without need for non-invasive or invasive mechanical ventilation, high flow oxygen, or Extracorporeal Membrane Oxygenation (ECMO) at Day 29

	The effect of alvelestat on clinical outcomes	
By treatment group (alvelestat/placebo):
 
 • Mortality rate at Day 90 • Proportion of subjects alive and free of respiratory failure (without need for non-invasive or invasive mechanical

Endpoints	Definitions

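### The respiratory-failure-free endpoint mixes patients who enter in failure with patients who enter free of it; its definition conflicts within the SAP, and no usable baseline term is specified

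*SAP*

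**What the plan says.** Eligibility (protocol 6.1) requires "A score of Grade 3 to 5 on the WHO 9-point Ordinal Scale". Protocol 9.3.2 describes score 5 as "severe disease, noninvasive ventilation or high flow oxygen".

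Respiratory failure is defined in two ways:

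- **Broad.** Protocol 9.3.1 records status as "Alive with respiratory failure (need for high-flow oxygen, Extracorporeal Membrane Oxygenation (ECMO), non-invasive or invasive mechanical ventilation". The protocol endpoint tables agree, and so does SAP Table 3: "without need for non-invasive or invasive mechanical ventilation, high flow oxygen, or Extracorporeal Membrane Oxygenation (ECMO) at Day 29".
- **Narrow.** The SAP 8.4.2 analysis list has "Proportion of patients alive and not in respiratory failure (invasive mechanical ventilation or ECMO (Days 10 and 29", and SAP Table 11 repeats this restriction.

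For the comparison, SAP 8.4.2 states: "Secondary endpoints assessing proportion of patients fulfilling an event will be compared between treatments using a logistic regression model adjusting for treatment". It then reports a stratum-weighted difference without naming a stratum and adds that, when events are few, "the baseline disease state will be dropped from the model". Protocol 10.3.2 plans counts and percentages for this endpoint, with a chi-square or Fisher test for categorical variables. Protocol 7.2 says "the randomization scheme will not be stratified".

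**The concern.** Under the broad definition the endpoint asks two different questions. A WHO 5 patient starts in failure, so success means that failure resolved. A WHO 3-4 patient starts free, so success means being still free at the visit. The plan files both under disease progression and pools them.

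The narrow definition does not remove the difficulty. The same SAP 8.4.2 list, under the same treatment-only sentence, compares oxygen use and non-invasive ventilation, and Table 11 adds high-flow oxygen to the latter. WHO 5 patients enter meeting both of these Table 11 needs, and WHO 4 patients enter already on oxygen.

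Protocol 10.1 wants the trial to look for signals on clinical outcome, and the amendment summary ties the Day 60 unblinding to a development decision. An arm that happens to receive more WHO 5 patients could look worse for that reason alone.

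**Working it through.** The documents give no power, event rate or expected number of patients at WHO 5, so there is no planned figure to reproduce. The sizes below are illustrations.

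**Inputs.** N = 15. Allocation is 2:1 in protocol 5.2 and 10.1 (10 and 5), but 1:1 in SAP 5.4 (7-8 per arm), so both 10:5 and 8:7 are shown. K, the number at WHO 5, is assumed to be 3 to 7. Day 29 success is assumed to be 90% at WHO 3-4 and 60% (range 70% to 40%) at WHO 5.

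**Step 1: is there a baseline term?** With treatment as the only term and no stratum, the weighted estimator reduces to the raw difference in proportions. The clause on few events implies that a baseline term was intended, but 8.4.2 does not say which variable it is or how it is coded. SAP 8.4 does adjust Day 29 recovery for COVID disease severity, yet 8.4.2 lists that same endpoint under the treatment-only sentence.

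**Step 2: chance imbalance.** With x of the K patients in the first arm (size n1, the other n2), P(x) = C(n1,x)·C(n2,K−x)/C(15,K). Sum over all x with |x/n1 − (K−x)/n2| ≥ 0.40.

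| K | 10:5 | 8:7 |
|---|---|---|
| 3 | 10/455 = 2% | 35/455 = 8% |
| 4 | 315/1365 = 23% | 105/1365 = 8% |
| 5 | 753/3003 = 25% | 357/3003 = 12% |
| 6 | 445/5005 = 9% | 595/5005 = 12% |
| 7 | 1815/6435 = 28% | 849/6435 = 13% |

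For example, at 10:5 with K = 5 the qualifying values are x = 5, 2, 1 and 0: 252 + 450 + 50 + 1 = 753. The jumps between rows arise because few splits are possible.

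**Step 3: effect on the outcome with no drug effect.** Spurious difference = imbalance × (success at WHO 3-4 − success at WHO 5).

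- 0.40 × (0.90 − 0.70) = 0.08
- 0.40 × (0.90 − 0.60) = 0.12
- 0.40 × (0.90 − 0.40) = 0.20

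If nobody had left their entry status, the limit would be 0.40 × (1 − 0) = 0.40. The early visits may lie closer to that limit.

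**Step 4: would a baseline term survive?** With K = 5 and 90%/60% success, expected failures are 10 × 0.10 + 5 × 0.40 = 3 of 15. The chance that at least one arm has no failures, at common success p, is p^n1 + p^n2 − p^15.

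- p = 0.80: 0.107 + 0.328 − 0.035 = 0.40 at 10:5, and 0.34 at 8:7
- p = 0.90: 0.349 + 0.590 − 0.206 = 0.73 at 10:5, and 0.70 at 8:7

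The clause that removes the baseline term would therefore often apply. If an arm without failures counts as having no events, SAP 8.4.2 leaves only raw proportions.

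**The case against.** Baseline is not absent from the plan, and a reader might wrongly infer that it is. SAP 8.4.2 mentions a baseline disease state and a stratum-weighted estimator. The most natural reading is that a term was left out of one sentence, not that baseline was ignored by decision. Descriptive material also helps:

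- SAP Table 6 gives WHO 3, 4 and 5 by arm, so an imbalance would be visible.
- SAP 8.4.2.1 covers new non-invasive ventilation or high-flow use.
- SAP 8.4.3 adjusts WHO change for the baseline score.
- SAP Figure 3 splits ordinal scores by baseline score.
- Protocol 10.3.2 plans shift tables of respiratory support.

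All of that stands. None of it gives this endpoint by baseline status, however. The 8.4.2.1 item on non-invasive ventilation and high-flow oxygen is limited to patients who are alive, and it does not show WHO 5 patients becoming free.

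It is also tempting to say that WHO 5 patients cannot progress to the endpoint. That does not hold for the analysis as listed in SAP 8.4.2: under its narrow definition they are not in failure at entry and can progress.

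Finally, a better test would gain little. Fisher power for 90% versus 60% is about 0.15 at 10:5 and 0.16 at 8:7. That argues for relying on the table rather than on any model.

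**Conclusion.** The point holds in limited form. Two definitions of respiratory failure conflict, and they differ on whether WHO 5 entrants start in failure. The baseline term in SAP 8.4.2 is implied, unspecified and removable when events are few.

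The resulting risk depends on an unknown K and on an allocation ratio that the two documents state differently. It is not right to quote only the figures near 25-28%: at 10:5 the chance falls to 9% for K = 6 and 2% for K = 3. A 40-point imbalance in baseline share is also not a 40-point outcome bias at Day 29; under the assumed rates it is 8-20 points.

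Priority is modest because the endpoint is secondary, the trial is unpowered, and efficacy is exploratory throughout.

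**What to change.** 1. Reconcile the respiratory-failure definition in SAP 8.4.2 and Table 11 with the protocol endpoint and SAP Table 3.
2. Tabulate the endpoint by arm within baseline WHO 3-4 (stayed free) and baseline WHO 5 (became free) at Days 5, 10, 29 and 60. Count deaths as failures, in line with the worst-case rule in SAP 7.4. This is the most useful change.
3. If an overall comparison is kept, name baseline WHO 5 versus 3-4 as the stratum and use an exact stratified test. Replace both the treatment-only sentence and the sentence on dropping the baseline state. Deleting the latter alone would remove the only explicit mention of a baseline term in 8.4.2.

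The cost is one split table, using a score that the schedule of assessments already collects at baseline, and a short SAP edit. The drawback is small cells, which should be shown as counts.

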10.3 Statistical Analyses

The main population for safety and tolerability analysis will be the Safety Set. The main population for efficacy analysis will be the Full Analysis Set; supportive analyses will also be performed using the Per-Protocol Set.

Continuous data will be presented using descriptive summaries (e.g., mean, standard deviation, minimum, maximum, median, lower quartile, and upper quartile). Categorical variables will be presented by the number of observations and relative (%) frequency.

Unless otherwise stated, baseline value for any variable will be the last value taken prior to the first dose of study medication.

Unless otherwise stated, all statistical tests will be 2-sided and conducted at the 5% level. All presented confidence intervals will be 2-sided 95% confidence intervals.

Handling of Missing Data

The study is designed to reduce the extent of missing data by alignment of assessments with routine clinical management where possible, by the use of clinical outcomes measures that are expected to be routinely collected for hospitalized patients with COVID-19 and use of telehealth assessments where appropriate to reduce the study burden on patients. However, missing data must be anticipated and handled as follows:

When a patient drops out of a trial full reporting of all reasons for their discontinuation will be collected.

For statistical analyzes missing values are considered a potential source of bias. A multiple imputation of missing data approach will be applied, using pattern mixture model methodology. Within each treatment, 4 proposed data patterns will be defined as follows:

- *Pattern 1: will include patients who completed treatment on study drug*
- *Pattern 2: will include patients who discontinue treatment early due to AEs*
- *Pattern 3: will include patients who discontinue treatment early due to lack of therapeutic efficacy (LOTE)*
- *Pattern 4: will include patients who discontinue treatment early due to reasons other than AE event or LOTE.*

The strategy for dealing with missing values will be further detailed in the statistical analysis plan. If the pattern of missing data is different to that envisaged, including following blinded review of the data at the end of the trial the strategy and the Statistical Analysis Plan (SAP) will be updated.

Descriptive statistical summaries will use Observed Case (OC) data and no missing data values will be imputed.

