7 GENERAL STATISTICAL CONSIDERATIONS

7.1 Sample Size

This is a pilot study and it is not powered based on any specific endpoint. Sample size has been set to minimize the number of patients exposed, but still large enough to give reliable estimates on the efficacy and safety of alvelestat in the target population.

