7.2 General Principles

This is a double-blind, placebo controlled randomized pilot study which may inform on treatment effect for future studies.

Descriptive statistics

Continuous variables will be summarized using descriptive statistics including number of non-missing observations (n), arithmetic mean (Mean), median (Median), standard deviation (SD), minimum value (Min) and maximum value (Max).

For categorical variables, summaries will include the number of non-missing observations (n) or the number of patients in the population (N) as applicable, the counts of subjects and percentages. Percentages will be rounded to one decimal place.

Statistical Analyses

All analyses are considered exploratory and hypothesis-generating. All tests will be two-sided at 5% significance level. Hypothesis tested for the primary endpoint will be if addition of alvelestat to SoC for up to 10 days will be safe and well tolerated as compared to standard of care plus placebo.

Secondary endpoints are tested independently and there will be no adjustment for multiple tests.

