- Change from baseline in desmosine/isodesmosine will be compared between treatments using ANCOVA models with treatment allocation as a factor and baseline desmosine/isodesmosine as a covariate. Estimated treatment difference with 95% confidence intervals and associated 2-sided p-value will be given.
- Biomarker values that are below the lower limit of quantitation of assay will be reported as the lower limit of quantitation (LLQ)/2.
- Biomarker values may be log transformed if appropriate.

The proportion of patients with recovery at Day 29 will be compared between treatment groups using a logistic regression model adjusting for treatment and COVID disease severity. The difference between treatment arms will be expressed as a difference in proportions as measured by the Cochran Mantel-Haenzel (stratum)-weighted estimator based on the fitted logistic regression model. The delta method will be used to calculate the standard error for the difference and the associated confidence interval [Ge, 2011]. In addition, the raw proportions per treatment group will be given. If 0 events in any of the groups only raw proportions will be given.

Summaries of the results of the secondary analysis for recovery are displayed in Table 10.

Table 10. COSTA analysis tables – Secondary Analysis (Recovery)

Table #	Table Name	Table Contents
	Proportion of Patients with Recovery at 29 Days, ITT	Overall and by Treatment Group 
 • By Age Group • By Sex • By COVID Disease Severity
	Proportion of Patients with Recovery at 29 Days, PP	Overall and by Treatment Group

Patients that die in the study will be handled as worst case in all analyses.

To have an evaluation using all patients we will count an event as the type of need or worse (e.g., patients with oxygen need; non-invasive ventilator need; ventilator need; or with death at time of evaluation will be counted as having data supporting oxygen need), and included in both denominator and numerator.

8.4.1 Time to a recovery state (Day 1 - Day 29; measured in days)

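### The SAP withholds its delta-method interval when an arm has no events but not when an arm is at 100%, where that arm's variance falls to zero

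*SAP*

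**What the plan says.** SAP 8.4 compares Day 29 recovery using "a logistic regression model adjusting for treatment and COVID disease severity" and expresses the result as a stratum-weighted difference in proportions. SAP 8.4.2 applies the same kind of estimator to a list of proportion endpoints, with this interval: "The delta method will be used to calculate the standard error for the difference and the associated confidence interval". Both sections carry one boundary rule: "If 0 events in any of the groups only raw proportions will be given".

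Several endpoints in the 8.4.2 list count a good outcome as the event: recovery at Days 29 and 60, improvement of one or two WHO categories, and being alive and not in respiratory failure. The others (oxygen use, non-invasive ventilation, death) count a bad outcome.

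The only other sparse-data instruction in 8.4.2 is "For endpoints with a low number of events, the baseline disease state will be dropped from the model". Protocol 10.3.2 names a chi-square or Fisher test for categorical variables, which gives a p-value but no alternative interval.

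**The concern.** The rule recognises that the interval fails at a boundary but covers only one end. When the event is a bad outcome, a very good arm has no events and the rule applies. When the event is a good outcome, the same very good arm has all events and the rule does not apply. Whether the interval is withheld therefore depends on how the outcome is labelled.

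At stake is the meaning of the printed interval. Protocol 10.3 states that "All presented confidence intervals will be 2-sided 95% confidence intervals", and SAP 7.1 describes the sample as "large enough to give reliable estimates on the efficacy and safety of alvelestat in the target population". In a 15-patient pilot the interval is the main statement of uncertainty. A zero-width interval, or one that excludes zero because an arm was treated as having no variance, would misstate it.

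**Working it through.** **Inputs.** The split is 10 alvelestat : 5 placebo (protocol 5.2, 10.1) or 7-8 per arm (SAP 5.4). The two documents conflict, so both are computed, writing the SAP split as 8:7. The interval is two-sided 95%, z = 1.96. The documents give no rate for the favourable endpoints. As an assumption, equal true rates in both arms of 1 - 0.235 = 0.765 to 1 - 0.149 = 0.851 are used, taken as survival from the case fatality ratios in protocol 5.8. The plan states no width or coverage figure to reproduce.

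**Step 1: treatment-only model.** The delta-method standard error of the risk difference equals SE = sqrt[p1(1-p1)/n1 + p2(1-p2)/n2]. An arm with p = 1 contributes 0. For 7/10 v 5/5:

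- SE = sqrt(0.7 x 0.3/10 + 0) = 0.1449; interval -0.300 ± 1.96 x 0.1449 = -0.584 to -0.016.
- Newcombe combines the Wilson limits (0.397 to 0.892 for 7/10; 0.566 to 1 for 5/5). Lower: -0.300 - sqrt(0.303² + 0²) = -0.603. Upper: -0.300 + sqrt(0.192² + 0.434²) = +0.175.

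**Step 2: adding severity.** If an arm is at 100%, the treatment coefficient has no finite estimate and that arm's fitted risks go to 1 in every stratum. As an illustration with an assumed mix, let moderate be 4/5 v 3/3 and severe 3/5 v 2/2. The weights n1n0/n are 5x3/8 = 1.875 and 5x2/7 = 1.429, or 0.568 and 0.432 after scaling.

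- Difference = 0.568 x (-0.2) + 0.432 x (-0.4) = -0.286.
- SE = sqrt(0.568² x 0.16/5 + 0.432² x 0.24/5) = 0.139, all from the alvelestat arm.
- Interval -0.559 to -0.014. Dropping or keeping the covariate does not restore the missing variance.

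**Step 3: particular tables (alvelestat v placebo, unadjusted).**

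| Result | Planned interval | Newcombe | Fisher p |
|---|---|---|---|
| 10/10 v 5/5 | 0 to 0 | -0.28 to 0.43 | 1 |
| 7/10 v 5/5 | -0.584 to -0.016 | -0.60 to 0.18 | 0.505 |
| 6/10 v 5/5 | -0.704 to -0.096 | -0.69 to 0.09 | 0.231 |
| 5/8 v 7/7 | -0.71 to -0.04 | -0.69 to 0.05 | 0.20 |
| 10/10 v 3/5 | -0.029 to 0.829 | 0.004 to 0.769 | 0.095 |

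With exactly one arm at 100% and no arm at 0, the planned interval is narrower than Newcombe in 10 of 13 tables at 10:5 and 12 of 13 at 8:7. The exceptions are 10/10 v 1/5, 2/5 and 3/5, and 8/8 v 3/7.

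**Step 4: how often, for the unadjusted interval.** The chance that at least one arm is at 100% is p^10 + p^5 - p^15 at 10:5. At 0.765 this is 0.069 + 0.262 - 0.018 = 0.313; at 0.851 it is 0.199 + 0.446 - 0.089 = 0.557 (unrounded). At 8:7 the formula is p^8 + p^7 - p^15, giving 0.253 and 0.509. A 0-event arm, the case the rule covers, occurs in under 0.1% of trials at these rates.

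False exclusion of zero was obtained by summing exact binomial probabilities over all tables, with the 0-event rule applied:

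| Split | True rate, both arms | An arm at 100% | Planned interval excludes zero | Of which with a 100% arm | Newcombe throughout |
|---|---|---|---|---|---|
| 10:5 | 0.765 | 31% | 14.4% | 11.8 points | 4.9% |
| 10:5 | 0.851 | 56% | 9.4% | 8.4 points | 4.3% |
| 10:5 | 0.90 | 73% | 4.8% | 4.4 points | 3.2% |
| 8:7 | 0.765 | 25% | 9.6% | 6.9 points | 4.4% |
| 8:7 | 0.851 | 51% | 5.9% | 5.3 points | 2.7% |
| 8:7 | 0.90 | 70% | 3.1% | 2.9 points | 1.4% |

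At 0.90 both arms are at 100% in 0.9^15 = 20.6% of trials, so the interval is [0, 0]. It contains the true difference only because that difference was assumed to be zero. Given a 100% arm at 10:5, mean width is 0.37 against 0.74 for Newcombe.

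**The case against.** The strongest reply is that little depends on these intervals. SAP 7.2 says "All analyses are considered exploratory and hypothesis-generating". The trial is unpowered and no decision rule uses the intervals. Raw proportions are always printed, so [0, 0] beside 10/10 and 5/5 would look degenerate to any reader. Protocol 10.3.2 plans only counts and percentages for respiratory-failure-free status and WHO responders. All of this stands and limits the consequence. It does not make the stated 95% level correct, and 7/10 v 5/5 would not look degenerate.

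The rates are also a weak proxy. Survival in a cited inpatient cohort stands in for recovery, which the SAP does not formally define, and for WHO improvement. This stands too, so the frequencies are conditional on that assumption.

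Three stronger readings are tempting and are not supported:

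- *That a 100% arm always makes the interval too narrow.* The exceptions in step 3 show otherwise. For 10/10 v 3/5 the planned interval is the more cautious of the two.
- *That 8.4.2 fits treatment alone, so Day 29 recovery has two different models.* The section names only treatment, yet it also drops a baseline disease term when events are few and uses a stratum-weighted estimator. Its wording is ambiguous. The false-exclusion rates therefore describe the unadjusted interval only; for the adjusted one, the mechanism is shown but no frequencies.
- *That the method is biased against alvelestat.* At 10:5, the 100%-arm tables where the planned interval excludes zero but Newcombe and Fisher do not (5, 6 and 7/10 v 5/5) do point that way. At 1:1 the direction depends on which arm has 8 patients: 5/8 v 7/7 or 7/7 v 5/8.

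**Conclusion.** The gap is real in both sections and under either allocation. With an arm at 100%, the planned interval omits that arm's uncertainty. It has zero width when both arms are at 100%, is usually too narrow when one is, and can exclude zero without support from a score interval or Fisher's test.

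At the assumed equal rates of 0.765-0.851, most of the excess false exclusion of the unadjusted interval comes from 100% arms. At 0.9 and above, false exclusion is below 5% and the problem is width. Worth correcting before database lock, but the effect is misleading precision in exploratory results, not a wrong confirmatory decision. The 2:1 v 1:1 conflict between protocol and SAP is a separate matter and adds no weight here.

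**What to change.** In SAP 8.4 and 8.4.2, extend the boundary rule to any group with 0% or 100% events. In those cases, report raw proportions with a Newcombe or Miettinen-Nurminen 95% interval for the unadjusted risk difference in place of the delta-method interval. Use Fisher's exact test, already in protocol 10.3.2, for any test. The model-based estimate can stay where no arm is at a boundary. State whether the 8.4.2 model contains the baseline disease term, and specify the Day 29 recovery model once.

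The cost is a SAP wording change and simple programming. At the assumed rates, for the unadjusted interval, false exclusion would become 2.6 + 2.7 = 5.3% to 1.0 + 3.3 = 4.3% at 10:5, and 2.8 + 3.9 = 6.7% to 0.6 + 2.7 = 3.3% at 8:7. The first term comes from tables without a boundary arm and the second from Newcombe in tables with a 100% arm.

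The downside is that a score interval and Fisher's test can disagree, as for 10/10 v 3/5 in step 3, so the interval should be read as an estimate and not as a test. Giving raw proportions alone at 100% would be cheaper and would cut false exclusion to 2.6-1.0% (10:5) and 2.8-0.6% (8:7). But it would leave no interval in 31-56% and 25-51% of trials.
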